16 APPENDICES

Appendix 1

Output Conventions

TLF will be generated using SAS® and will be displayed on letter size paper with landscape orientation, 1-inch margins and 9 pt. Courier New font.

The header section will comprise the sponsor's name, the protocol number, the delivery description, the data cut-off date (if applicable), the TLF number, the TLF title, the analysis set, and the page number (Page X of Y). The footer section will include the TLF footnotes, the CRO's name, the date and time of the execution of the program, and the name of the program.

P-values equal to or above 0.0001 will be reported to 4 decimal places; p-values less than 0.0001 will be reported as “<0.0001”; p-values greater than 0.9999 will be reported as “>0.9999”.

The mean, median, geometric mean will be displayed to one more decimal place than the original value; Q1, Q3, minimum and maximum will keep the same number of decimal places as the original value; standard deviation, standard error, CV and CI will be displayed to two more decimal places than the original value. If derived parameters are to be summarized, the number of decimals of the derived values is to be chosen on a case-by-case basis, but the rule above applies.

For categorical summary tables, percentages will be reported to one decimal place. Percentages between 0 and 0.1 (both exclusive) will be displayed as “<0.1”. The denominator for each percentage will be the number of subjects within the population per treatment group unless otherwise specified.

Listings will be ordered by treatment group, subject number, date and visit (where applicable). Imputed dates will not be presented in the listings.

Dates & Times Format

Date and time (if available) will be presented in the format yyyy-mm-dd/hh:mm.

Presentation of Treatment Groups

When applicable, study treatments will be represented as follows in the different outputs:

Study Treatment Full Name	Study Treatment Output Name
Roflumilast cream 0.15%	Roflumilast Cream 0.15%
Vehicle cream	Vehicle

	STATISTICAL ANALYSIS PLAN, Version 3.0
Protocol Number: ARQ-151-311	Sponsor: Arcutis Biotherapeutics, Inc.

Appendix 2

Algorithm for Imputation of Start/End Date and Time of Adverse Events and Prior/Concomitant Medications

Event Start Date Imputation

- Imputation of event end date should be done before imputation of event start date.
- Completely missing: Impute to the first study treatment date.
- Missing day and month: Impute to January 1st, unless year is the same as year of first study treatment dose date then impute to the first study treatment date.
- Missing day: Impute to the 1st day of the month, unless month and year are the same as month and year of first study treatment dose date then impute to the first study treatment date.
- If imputed event start date is after event end date (imputed or not), set the event start date to the imputed event end date.

Event Start Time Imputation (for Adverse Events only)

Imputation of event end time should be done before imputation of event start date.

- If the event date is not the same as the first dose date or time part of the first dose date is missing, impute to 00:00.
- If the event date is the same as the first dose date and event occurred prior to study drug application (as flagged in CRF), impute to 00:00.
- If the event date is the same as the first dose date and event did not occur prior to study drug application (as flagged in CRF), impute to time part of first dose date.
- If the event start date is equal to event end date and imputed event start time is after event end time (imputed or not), set the event start time to the imputed event end time.

Event End Date Imputation

- Completely missing (and not flagged as “ongoing”): Impute to the last contact date.
- Missing day and month: Impute to December 31st, unless year is the same as last contact date then impute to the last contact date.
- Missing day: Impute to the last day of the month, unless year and month are the same as year and month of last contact date then impute to the last contact date.

Event End Time Imputation (for Adverse Events only)

Impute to 23:59.

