3 STUDY DESIGN

3.1 Overall Design

[figure not shown]
This is a Phase 3, parallel group, double blind, vehicle-controlled study in which Roflumilast cream 0.15% or vehicle is applied QD x 4 weeks to subjects with mild to moderate atopic dermatitis.

- Upon determination of eligibility, subjects will be randomized 2:1 to either Roflumilast cream 0.15% or matching vehicle cream. The randomization will be stratified by vIGA-AD score at baseline ('Mild' vs. 'Moderate') and by study site.
- At the Week 4 visit, subjects may be eligible to enroll in an open label extension study (ARQ-151-313) in which they will receive Roflumilast cream 0.15% QD.

The trial design is represented schematically in [Figure 1](#).

	STATISTICAL ANALYSIS PLAN, Version 3.0
Protocol Number: ARQ-151-311	Sponsor: Arcutis Biotherapeutics, Inc.

Figure 1 Study Schema

A Phase 3, 4-Week, Parallel Group, Double Blind, Vehicle-Controlled Study of the Safety and Efficacy of ARQ-151 Cream 0.15% Administered QD in Subjects with Atopic Dermatitis

Approximately 650 subjects with atopic dermatitis will be randomized 2:1 to receive either:

- Roflumilast cream 0.15% or Vehicle cream

Subjects will have $\geq 3\%$ BSA involvement (excluding the scalp, palms, soles) with a vIGA-AD score of '2' (mild) or '3' (moderate) for study entry

Up to 50% of the subjects will be ≥ 18 years old

	STATISTICAL ANALYSIS PLAN, Version 3.0
Protocol Number: ARQ-151-311	Sponsor: Arcutis Biotherapeutics, Inc.

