h Adolescents and adults will complete the C-SSRS (12 years of age and older). Adults will complete the PHQ-8. Adolescents (ages 12 to 17, inclusive) will complete the PHQ-A (PHQ-9 modified). Parents/caregivers will complete CDI-2 (parent report) for children 6-11 years of age, inclusive.

i The DLQI will be completed by subjects ≥ 17 years of age. The CDLQI will be completed for subjects 6 to 16 years old, inclusive. The Dermatitis Family Impact Questionnaire (DFI) will be completed by parents/caregivers for all subjects 6 to ≤ 17 years of age.

j Photography of AD lesion(s) selected by the Investigator will be performed at all investigational sites. All efforts will be made to de-identify the subjects. Canfield equipment will be used to capture photographs. Subjects who are unwilling to participate in the medical photography will be allowed to opt out of this procedure, as documented on the Informed Consent Form.

	STATISTICAL ANALYSIS PLAN, Version 3.0
Protocol Number: ARQ-151-311	Sponsor: Arcutis Biotherapeutics, Inc.

^k A urine pregnancy test will be administered to all females of child-bearing potential. A negative result is required for continued participation in the study, and results must be available prior to dispensing of study drug at each visit.

^l For all subjects entering this study under Amendment 2, a single PK trough draw will be collected at Day 29 only for subjects \geq 12 years old. Ensure study medication was not applied in the area where PK will be drawn.

^m Subjects to apply assigned IP during clinic visits, except for the Day 29/ET visit.

ⁿ It is expected that kits will be dispensed based on %BSA affected. See IP Handling Manual for details.

^o On Day 8 and 15, dispensing of IP is optional. Site should review IP kit to ensure sufficient IP is available until the next visit and only dispense additional IP if needed. On Day 29, if the subject is unable to perform the Day 29 clinic visit due to COVID-19 restrictions (isolation, quarantine, etc.) then additional IP may need to be dispensed so IP can continue to be applied at home until the subject is able to return to the clinic to complete the Day 29 assessments (see IP Handling Manual for the process to dispense additional IP at or after Day 29).

^p Every tube should be weighed and recorded when dispensed and returned. See IP Handling Manual for details.

^q Compliance determination is described in the IP Handling Manual

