12.1.3 Primary Endpoint Analysis

For the primary analysis, missing vIGA-AD scores will be imputed using multiple imputation as described in Section 6.2.1. These imputations will result in a minimum of 25 to a maximum of 250 complete analysis datasets, depending on the number of imputed monotone datasets that are required.

Percentages of subjects having a vIGA-AD Success (refer to Section 12.1.1) will be presented by visit and treatment group based on multiply imputed data in the ITT population along with a 95% Wilson CI. The common MH odds ratio and common MH proportion difference, adjusted for the randomization factors (i.e., randomized vIGA-AD score and pooled study site) will also be provided along with their common associated 95% CIs. Additionally, count and percentage of subjects having a vIGA-AD success, count and percentage of subjects in each category of the vIGA-AD scale, and descriptive statistics for the vIGA-AD scores, change in vIGA-AD score from

	STATISTICAL ANALYSIS PLAN, Version 3.0
Protocol Number: ARQ-151-311	Sponsor: Arcutis Biotherapeutics, Inc.

baseline and percent change in vIGA-AD score from baseline will be presented by visit and treatment group based on observed data in the ITT population.

The primary endpoint (vIGA-AD Success at Week 4) will then be analyzed using multiple imputation CMH test stratified by the randomization factors. To do so, a CMH analysis will be performed separately for each of the complete multiply imputed analysis data sets, and results will be combined into one multiple imputation inference using the methodology described in Section 6.2.1. Statistical significance will be concluded at the 5% significance level (2-sided). Should the odds ratio be not estimable for at least one multiply imputed dataset, the conclusion of the study will be based on the p-value obtained from a MH test, stratified by the randomization factors, for the common MH proportion difference at Week 4.

The following sensitivity analyses to the primary analysis of the primary endpoint will be performed:

- Multiply-imputed data (refer to Section 6.2.1) on mITT population (refer to Section 4.2) and
- Tipping Point analysis (refer to Section 6.2.3) on ITT population.
- Non-responder imputation (refer to Section 6.2.2) on ITT population.
- Observed data on ITT population (refer to Section 4.1).
- Observed data on PP population (refer to Section 4.3).

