13 SAFETY ANALYSIS

Safety analyses will be conducted using the safety population. Subjects will be analyzed based on the treatment received and the stratum they belong to.

No formal inferential statistics will be performed on safety assessments.

Also, treatment-emergent adverse events by SOC and PT table and summary of weight change will be presented by treatment groups for age 6 to 17 years and ≥ 18 years separately.

	STATISTICAL ANALYSIS PLAN, Version 3.0
Protocol Number: ARQ-151-311	Sponsor: Arcutis Biotherapeutics, Inc.

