13.4 Local Tolerability Assessments

The investigator's assessment of the application site reaction will be summarized by visit using both categorical methods (number and percentage of subject with each score) as well as continuous methods (e.g., mean, standard deviation, etc.)

Local tolerability (burning/stinging sensation) assessed by the subject will be summarized using number and percentage similarly.

13.5 Patient Health Questionnaire Depression Scale (PHQ-8) and Patient Health Questionnaire Depression Scale (Modified PHQ-A)

The Modified PHQ-A Assessment will be performed in adolescent subjects (12-17 years old, inclusive; question 9 has been removed since that is better evaluated by use of the C-SSRS tool).

The PHQ-8/Modified PHQ-A score is the sum of the responses for the questions, each question ranging from 0 (Not at all) to 3 – (Nearly every day). Five severity categories of depression are defined as follows:

- None – Minimal depression (0 to 4)
- Mild depression (5 to 9)
- Moderate depression (10 to 14)
- Moderately severe depression (15 to 19)
- Severe depression (20 to 24)

The score will be set to missing in case of at least one missing value. The number and percentage of subjects in each category will be summarized by treatment and visit. A summary of the shifts in depression category from baseline to each study visit will also be provided.

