13.7 Columbia-Suicide Severity Rating Scale (C-SSRS)

The Columbia-Suicide Severity Rating Scale (C-SSRS) is a questionnaire used (for adolescents and adults 12 years old and older) for suicide assessment developed by multiple institutions, including Columbia University. The C-SSRS prospectively assesses Suicidal Ideation and Suicidal Behavior. At the Screening study visit, “Baseline/Screening” version of the C-SSRS will be used. This version assesses Suicidal Ideation and Suicidal Behavior during the subject’s lifetime and during the past 6 months. For the Screening visit, “lifetime” experience of the subject with Suicidal Ideation and Suicidal Behavior will be summarized. On all subsequent visits, the “Since Last Visit” version will be used (Baseline/Day 1, Week 1/Day 8, Week 2/Day 15 or Week 4/Day 29).

Tables will include results from the Suicidal Ideation and Suicidal Behavior sections of the C-SSRS. Frequencies and percentages of subjects with a response of “Yes” at any point on the Suicidal Ideation and Suicidal Behavior items will be summarized by study visit and treatment group.

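### The SAP's default percentage denominator counts subjects who were never given the age-restricted depression, suicidality and urinalysis assessments, so printed absolute percentages are too small

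*SAP*

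**What the plan says.** SAP Appendix 1 (Output Conventions) gives the rule for categorical tables: "The denominator for each percentage will be the number of subjects within the population per treatment group unless otherwise specified". SAP Section 13 fixes the population: "Safety analyses will be conducted using the safety population". Section 4.7 defines that population without any age limit.

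The instruments are limited by age (SAP Table 1, footnote h). Adults complete the PHQ-8, ages 12–17 the modified PHQ-A, and ages 12 and over the C-SSRS. For the youngest group, "Parents/caregivers will complete CDI-2 (parent report) for children 6-11 years of age, inclusive". Footnote b adds that, for subjects entering under Amendment 2, laboratory samples after Screening are taken only from those aged 12 or over.

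The table specifications name no denominator:

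- Section 13.5 (PHQ-8 and modified PHQ-A): "The number and percentage of subjects in each category will be summarized by treatment and visit", plus shifts in category from baseline.
- Section 13.6 (CDI-2): the proportion in each category by arm and visit, plus shifts.
- Section 13.7 (C-SSRS): "Frequencies and percentages of subjects with a response of" Yes to the ideation and behavior items, by visit and arm.
- Section 13.2 (qualitative urinalysis): number and percentage at each result level, by arm and scheduled visit.

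Elsewhere the SAP does set its own base. Section 7.1 uses randomized subjects for disposition, and the laboratory shift tables in 13.2 are limited to subjects with both a baseline and a visit result.

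**The concern.** Appendix 1 applies unless something else is specified, and in these four places nothing is. A programmer following the SAP would divide the number of adults with a raised PHQ-8 score by everyone in the arm, including children and adolescents who never saw the form. The categories in such a table would not add to 100%.

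These are not incidental tables. Protocol Section 2.3.7 reports psychiatric adverse events in 5.9% of patients on the oral drug against 3.3% on placebo, with some cases of suicidal ideation and completed suicide. Subjects with a PHQ-8 or PHQ-A score of 10 or more, or with C-SSRS ideation or behavior, are excluded at entry. Later positives will therefore probably be few and will be read as small percentages. A small percentage halved by its denominator gives false reassurance about the absolute rate.

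**Working it through.** The plan states no diluted percentage or age-eligible denominator, so there is no figure of its own to reproduce.

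**Inputs.** Planned size and allocation: "Approximately 650 subjects with atopic dermatitis will be randomized 2:1 to receive either" active or vehicle (SAP 3.1), so about 650 × 2/3 = 433 active and 650/3 = 217 vehicle. Adult share: "Up to 50% of the subjects will be" aged 18 or over (SAP 3.1). The split between ages 6–11 and 12–17 is not given, so it is assumed and varied below.

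**Formula.** Let s be the share of the arm eligible for the instrument and m the share of eligible subjects with no result at the visit. Then

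printed % = true % × s × (1 − m), and the dilution factor with no missing data is 1/s.

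A between-arm difference of d points prints as about s × d. The ratio between arms is unchanged if s and m are equal in the two arms.

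**PHQ-8 in its own table.** With s at most 0.50, the factor is at least 1/0.50 = 2.0. Take an illustrative true rate of 5.0% and adults at 50%. The active arm has 433.3 × 0.50 = 216.7 adults and 216.7 × 0.05 = 10.8 cases, and 10.8/433.3 prints as 2.5%. With an assumed 10% of adults missing the visit it prints as 5.0 × 0.50 × 0.90 = 2.25%.

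**All instruments, assumed age mixes within the 50% cap.**

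| Adults / 6–11 / 12–17 (%) | PHQ-8 | PHQ-A | CDI-2 | C-SSRS |
|---|---|---|---|---|
| 50 / 20 / 30 | 2.0 | 3.33 | 5.0 | 1.25 |
| 50 / 30 / 20 | 2.0 | 5.0 | 3.33 | 1.43 |
| 40 / 40 / 20 | 2.5 | 5.0 | 2.5 | 1.67 |
| 25 / 50 / 25 | 4.0 | 4.0 | 2.0 | 2.0 |
| 25 / 60 / 15 | 4.0 | 6.67 | 1.67 | 2.5 |
| 25 / 20 / 55 | 4.0 | 1.82 | 5.0 | 1.25 |

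The C-SSRS factor is 1/(1 − share aged 6–11), so 20–60% gives 1.25 to 2.5. With adults at the 50% cap it cannot exceed 2.0. If the PHQ-8 and PHQ-A are pooled in one table, as 13.5 could be read, the pooled factor equals the C-SSRS factor. For urinalysis after Screening the factor is 1/(1 − share who are under 12 and entered under Amendment 2), which is no larger than the C-SSRS factor.

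**How well ratios are kept.** Age is not a stratification factor. With 50% adults, the 95% range for the chance difference in adult share between arms is 1.96 × 0.5 × √(1/433 + 1/217) = 0.08, or about ±8 points. Holding the overall share at 50%, that gives 52.7% against 44.6% (ratio 1.18) or 47.3% against 55.4% (ratio 0.85). A printed PHQ-8 ratio could therefore move by 15–18% from age imbalance alone.

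**After the fix.** With eligible, assessed subjects as the base, the factor is 1.0 for every instrument and the 5.0% prints as 5.0%.

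**The case against.** The best defense is that Appendix 1 is only a default. Table layouts are in a separate document (SAP Section 5) that is not available here and may set sensible denominators. Sections 13.5 to 13.7 also state the age band for the PHQ-A, CDI-2 and C-SSRS, which a careful programmer might take as the base. That is possible, but stating who completes a form does not name a denominator, and nothing in the SAP says the layouts override the default.

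The limits on impact do stand:

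- Counts are printed beside the PHQ and C-SSRS percentages, and Section 8 tabulates age groups for the safety population, so an approximate rate can be recovered.
- CDI-2 scores and changes are also summarized descriptively, without this denominator.
- Section 13 plans no safety inference, and the adverse event tables, which carry psychiatric events, are unaffected.

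A reader might infer three stronger things that the documents do not support.

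1. *Two-fold dilution or more for every instrument, suicidality included.* Only the PHQ-8 in its own table is assured of that. The C-SSRS covers everyone aged 12 or over, so two-fold dilution needs at least half of subjects to be aged 6–11, which no document states.
2. *A four-fold PHQ-8 factor from the protocol's 25% adult cap.* The supplied protocol is the original version. The SAP follows Amendment 4 and states 50%, so that is the limit to use.
3. *Observed-case efficacy percentages turning into non-responder percentages.* Section 12.1.3 has results "presented by visit and treatment group based on observed data in the ITT population" without naming the base. If all ITT subjects were used, an assumed 10% missing would turn 37% into 33.3%. But Section 5.5 sets subjects who discontinue for an adverse event or lack of efficacy to missing for observed-case analyses, Section 12.3 says there is no imputation for the exploratory endpoints, and 12.1.3 and 12.5 list non-responder imputation as a separate analysis. These point to excluding missing subjects.

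**Conclusion.** The point holds for the tables in 13.5 to 13.7 and the qualitative urinalysis table in 13.2. Followed as written, the SAP puts subjects who were never assessed into the denominator, and absolute percentages and between-arm differences come out too small. The factor is at least 2.0 for the PHQ-8 tabulated separately. That assumes the 50% adult cap is kept, and chance imbalance could put one arm slightly on the other side of it. For the other assessments the size depends on an age mix the documents do not give, so the figures in the table above are illustrations. Between-arm ratios are approximately preserved, apart from chance age imbalance and unequal missed visits.

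This is a defect in how safety results would be presented. It does not bias the treatment comparison in a set direction, and it leaves the multiple-imputation efficacy percentages alone, because those datasets are complete. The observed-case base is a matter for clarification, not an error. The change should be made before the tables are produced, since the rule is explicit and the affected tables concern a known risk of the oral drug.

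**What to change.** Add to Appendix 1, and refer to it in 13.2 and 13.5 to 13.7: *For by-visit categorical tables, the denominator is the number of subjects in the arm, within the age group to which the assessment applies, with a non-missing result at that visit; shift tables also require a non-missing baseline result.* Print that denominator in each table, and state in 13.5 whether the PHQ-8 and modified PHQ-A are tabulated separately or together.

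As a clarification only, add to 12.1 to 12.3 that observed-case efficacy percentages use subjects with an observed value at that visit.

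The cost is SAP and table-layout wording. No data collection, sample size or inferential analysis changes.
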